9.5 Primary Endpoint

The primary endpoint is the risk of developing EFAD defined as defined by Figure in Appendix 3.

- The risk of developing EFAD in pediatric patients will be summarized by treatment group as frequency and percentage. Time to developing EFAD will be analyzed using the Kaplan-Meier approach.
- Both incidence rate and proportion of EFAD will be computed for each treatment group.
- The incidence rate of EFAD will be computed as the number of patients who develop EFAD during the Study Treatment Period divided by the corresponding person time (i.e. "person-day" which is computed as "total number of patients" times "treatment exposure period [day]" in the corresponding treatment group), and reported as per 100 patient days.
- The proportion of EFAD will be computed as the number of patients who develop EFAD during the Study Treatment Period divided by the corresponding total number of patients.

- The Holman Index will be summarized with descriptive statistics (number of patients, mean, standard deviation, median, minimum, and maximum) on an approximately 15-day basis in each of the 2 treatment groups (Clinolipid vs Intralipid).
- FA profiles will be summarized using descriptive statistics (number of patients, mean, standard deviation, median, minimum, and maximum) in each of the 2 treatment groups (Clinolipid vs Intralipid), as well as descriptive statistics of genetic polymorphisms in the FADS1 and FADS2 genes.

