1.5.1 Definition of Analysis Populations

Full analysis set (FAS): all patients who are randomized to receive either Clinolipid or standard of care soybean oil-based lipid emulsion (Intralipid) and have received at least one randomized study treatment. This dataset will follow the intent-to-treat principle and will analyze patients by planned randomized arm.

Per protocol set (PPS): all patients in the FAS who have Holman Index measurements taken at baseline and at least 1 other timepoint post-baseline, who have received a minimum of 7 days of ILE treatment, and are without a major protocol violation (i.e. violation that potentially impacts the primary endpoint).

Deviations that could be considered for exclusion in a PP analysis

- Randomization or treatment errors
- Investigational product not handled properly
- Key exclusion criteria such as:
 - Patients with liver disease including cholestasis
 - Patients with severe hyperlipidemia or severe disorders of lipid metabolism
 - Patients who are unable to tolerate necessary laboratory monitoring
 - Patient requires or is expected to require propofol for sedation

Deviations that should **not** lead to exclusion of data in a PP analysis

- Patients who violate inclusion/exclusion criteria relating to patient safety
- Missed informed consent signature/date
- Any deviation that does not directly impact the primary endpoint

Safety analysis set (SS): the set of all patients who have been administered study treatment (Clinolipid or Intralipid). Patients will be analyzed according to treatment received.

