2.4.1.1 Derivation of Primary Endpoint

The primary endpoint is the incidence of EFAD which is defined in the protocol and will be derived based on the Holman Index (Triene/Tetraene Ratio) provided by the central laboratory.

- Holman Index <0.2: normal EFA
- Holman Index 0.2 0.4: at risk for EFAD
- Holman Index >0.4: EFAD

A patient will be considered 'at risk for developing EFAD' if they have a Holman Index of 0.2 - 0.4 at any timepoint during the study treatment.

A patient will be considered as an incident of EFAD (the 'event') if they have a Holman Index >0.4 at any timepoint during the study treatment.

For time to EFAD Kaplan Meier analyses, the index time will be the start of treatment. The first incident of EFAD will be considered the event and will use the date of EFAD (date first lab with Holman Index >0.4 reported). Patients will be censored if they do not develop EFAD during their follow-up or if they die before developing EFAD at the time of their last Holman Index laboratory measurement. Time to EFAD will be calculated for each patient who develops EFAD as follows and standardized to days:

The incidence rate of EFAD (events per 100 patient days) will be calculated as the following per treatment group:

```
Number of patients developing EFAD * 100
Total patient days
```

The total number of patient days will be calculated per treatment group as follows:

$$\sum_{i=1}^{n} (Date of First EFAD Occurrence or End Date of Treatment)$$

- Start Date of Treatment)_i + 1

Where n is the total number of patients per treatment group. If a patient develops EFAD, then the date of first EFAD occurrence will be used, and if they do not, then end date of treatment will be used. If more than one instance of EFAD occurs, the patient will be counted once and the date of first occurrence will be used. This will then be standardized to days.

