2.4.1.2 Analysis of Primary Endpoint

Holman index scores will be summarized descriptively by timepoint per treatment group using n, mean, standard deviation, minimum, Q1, median, Q3, and maximum.

The frequency and percentage of patients at risk of developing EFAD (Holman Index 0.2-0.4) as well as those who developed EFAD (Holman Index >0.4) will be summarized by timepoint and at the maximum by treatment group. The denominator for the percentage of patients will be the number of patients in the population who had at least one post-baseline Holman Index measurement available. The incidence rate (per 100 patient days) of EFAD will also be calculated per treatment group.

If there are more than 5 cases of EFAD per arm, then time to develop EFAD will be analyzed using survival analysis approach (cumulative incidence), and the mean, standard error, Q1, median, Q3, minimum, and maximum for each treatment group will be displayed, where calculable. A cumulative incidence plot will also be produced. If there are less than 5 cases of EFAD in each treatment arm, then time to developing EFAD will be summarized descriptively by treatment group using n, mean, standard deviation, minimum, Q1, median, Q3, and maximum. If no events occur, then time to EFAD will not be calculated.

A spaghetti plot consisting of Holman index values over time will be produced with one line representing each patient, and different types of lines or symbols (e.g. solid and dashed) representing each treatment group. Two bolded lines will be added at y=0.2 and y=0.4 to represent the bounds for being at risk of EFAD and developing EFAD.

As a supportive analysis to the primary endpoint, the following will be analyzed:

• FA profiles will be summarized using descriptive statistics (number of patients, mean, standard deviation, median, minimum, and maximum) in each of the 2 treatment groups (Clinolipid vs Intralipid), as well as descriptive statistics of genetic polymorphisms in the FADS1 and FADS2 genes for the patients with buccal swabs with the 5 highest and 5 lowest arachidonic acid values in each treatment group.

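### In the FAS, the EFAD rate counts treatment days on which no event could be detected, while the SAP's percentage and Kaplan-Meier leave them out; the rate can err only downward, by an unknown amount

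*SAP*

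**What the plan says.** SAP 2.4.1.1 derives EFAD solely from the central-laboratory Holman Index. The SAP then summarises this one endpoint in three ways, each with its own risk set.

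- **Rate per 100 patient-days (SAP 2.4.1.1).** The numerator is "Number of patients developing EFAD * 100". The denominator sums days from start of treatment to first EFAD; for patients who do not develop it, "if they do not, then end date of treatment will be used". The sum has no sampling requirement: "Where n is the total number of patients per treatment group".
- **Kaplan-Meier (SAP 2.4.1.1).** Patients without EFAD are censored "at the time of their last Holman Index laboratory measurement". Under SAP 2.4.1.2 the survival analysis is run only when each arm has over five cases.
- **Percentage (SAP 2.4.1.2).** The denominator is "the number of patients in the population who had at least one post-baseline Holman Index measurement available".

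The primary analysis uses the FAS. SAP 1.5.1 defines this as patients who were randomized and "have received at least one randomized study treatment"; no Holman value is needed. SAP 2.6.2 imputes nothing except weight.

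Protocol 9.5 also bears on this. Its proportion is cases "divided by the corresponding total number of patients", and its person-time is built from all patients and their treatment exposure. SAP section 3 declares no changes from the protocol.

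**The concern.** A day can contribute an EFAD event only if a Holman sample is taken on or after it. Two kinds of treatment day in the FAS rate fail that test: all days of a patient with no sample after baseline, and the days between a patient's last sample and the end of treatment. Both enlarge the denominator and neither can enlarge the numerator.

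Such patients are foreseeable. SAP 2.2 lists a missing Holman value among the reasons for removal from the PPS, and the percentage denominator presupposes them. Treatment may be as short as 7 days, and the first scheduled sample after baseline is at Day 15. A patient who stops before then depends on a single end-of-treatment sample.

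The rate is a named result for the primary endpoint, and here an error toward low risk is the unwelcome direction. If samples are missed more often in one arm, the descriptive contrast between arms shifts for a reason unrelated to EFAD. With few cases the survival analysis is not run, so the rate and the percentage, which rest on different patients, carry the result.

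**Working it through.** **Nothing to reproduce.** The documents give no EFAD rate, event count or frequency of missed samples. The sample size is a feasibility number (50 per arm, SAP 1.4.2). The check is how far the SAP formula moves under stated assumptions.

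**Inputs.** From the SAP: n = 50 in one arm, and the rate formula. Assumed: E = 3 cases, each on day 15; *m* patients with no sample after baseline, treated *d* days each; the other 47 − *m* non-cases treated 20 days each; a fraction *q* of those last sampled *g* days before stopping.

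**Formulas.**
- SAP days = 3×15 + *m*×*d* + (47 − *m*)×20
- Observed days = 3×15 + (47 − *m*)×20 − *q*×(47 − *m*)×*g*
- Rate = 100×3 / days; shortfall = 1 − observed days / SAP days

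| Assumption | SAP days | Observed days | SAP rate | Observed-time rate | SAP rate low by |
|---|---|---|---|---|---|
| (a) all sampled on last treatment day | 45+940 = 985 | 985 | 0.305 | 0.305 | 0% |
| (b) all sampled, each 2 days before stopping | 985 | 985−94 = 891 | 0.305 | 0.337 | 9.5% |
| (c) m=5, d=7, no gap | 45+35+840 = 920 | 885 | 0.326 | 0.339 | 3.8% |
| (d) as (c), 2-day gap in all others | 920 | 885−84 = 801 | 0.326 | 0.375 | 12.9% |
| (e) m=10, d=10, no gap | 45+100+740 = 885 | 785 | 0.339 | 0.382 | 11.3% |
| (f) as (e), a quarter with a 5-day gap | 885 | 785−46.25 = 738.75 | 0.339 | 0.406 | 16.5% |

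An extreme case has m=15, d=10, the others treated 15 days and half of them with a 5-day gap. SAP days are 45+150+480 = 675 and observed days 675−150−80 = 445. The rates are 0.444 and 0.674, so the SAP rate is 34.1% low. Doubling the cases to 6 in (f) gives 0.690 against 0.825 (16.4% low), so the relative error hardly depends on the case count.

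**Between arms.** Suppose both arms have a true rate of 0.300 per 100 observed days, 20 days per sampled patient and 10 per unsampled patient. With 5 unsampled of 50, the SAP formula gives 0.300×900/950 = 0.284. With 15 it gives 0.300×700/850 = 0.247. The ratio is 0.247/0.284 = 0.87, an apparent 13% difference with identical risk.

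**Percentage beside the rate.** With 10 unsampled, the SAP percentage is 3/40 = 7.5% and the Protocol 9.5 proportion is 3/50 = 6.0%. The SAP rate still uses the days of all 50.

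**The case against.** Several points on the other side are sound.

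- **The rate follows the protocol.** Protocol 9.5 defines person-time by all patients and treatment exposure, and the PNALD and adverse-event rates use a similar exposure basis. A reader might infer that the SAP changed the rate. It did not; what it changed without saying so is the proportion's denominator.
- **The schedule is meant to prevent the gap.** Protocol 7.2.4 puts a Holman sample within 2 days of the last treatment day, whenever that falls. Protocol 6.14 asks for end-of-treatment procedures on withdrawal or discontinuation. If this is done, few patients lack a sample, and a sample taken on or after the last treatment day leaves no tail. This stands, but it is an intention: the SAP itself plans for missing values, and a sample up to 2 days early still leaves a tail, as in (b).
- **The results can be reconciled.** A reader might infer that the rate and percentage cannot be reconciled. The denominators are stated, Holman values and exposure are listed by patient, and PPS exclusions are counted by reason. The PPS requires a Holman value after baseline, so unsampled patients cannot enter it. The FAS nevertheless remains the primary set, and tail days remain in both.
- **The shift is small against the noise.** For 3 cases in 885 days the exact Poisson 95% limits are 0.619/885 and 8.767/885, or 0.07 to 0.99 per 100 days, against a shift in (f) of 0.406 − 0.339 = 0.067. No hypothesis test is planned, so no decision rule is affected. True, but this error has a known direction and is cheap to remove.

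**Conclusion.** The point holds for the FAS rate. It counts days on which EFAD could not be recorded, while the SAP percentage drops the unsampled patients and the Kaplan-Meier, if run, stops at the last sample. The error can only be downward, and it differs between arms if missed sampling differs.

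Its size cannot be fixed from the documents. It is zero if everyone is sampled on the last treatment day. With 5 to 10 of 50 patients unsampled, with or without short gaps, it is 3.8% to 16.5%. Those figures rest on the assumed treatment lengths, gaps and event days above.

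Two stronger readings are not supported. Nothing shows that the rate will be wrong by any particular percentage, and nothing shows that either product would be favoured, because the documents give no reason to expect more missed samples in one arm. The undeclared change to the proportion's denominator is certain whatever the missingness, since Protocol 9.5, SAP 2.4.1.2 and SAP section 3 cannot all stand as written.

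**What to change.** - **SAP 2.4.1.1:** calculate the rate over patients with a Holman value after baseline. End each non-case's time at the last Holman sample, or at end of treatment if that is earlier. The cap is needed because an end-of-treatment sample may be taken up to 2 days after the last dose, and ending time there would add off-treatment days.
- **Samples in that 2-day window:** state one rule for whether a value counts and which date is used, and apply it equally to cases and non-cases.
- **Supplementary results:** keep the Protocol 9.5 exposure-based rate and all-patient proportion alongside.
- **Reporting:** give, by arm, the number of treated patients with no Holman value after baseline and their treatment days.
- **SAP section 3:** list both denominator changes, the proportion's (already made) and the rate's (made by this fix).

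The cost is SAP wording, one derived date and a few extra table rows, with no new data. The main rate becomes slightly less favourable wherever samples were missed.

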2.4.1.2 Analysis of Primary Endpoint

Holman index scores will be summarized descriptively by timepoint per treatment group using n, mean, standard deviation, minimum, Q1, median, Q3, and maximum.

The frequency and percentage of patients at risk of developing EFAD (Holman Index 0.2-0.4) as well as those who developed EFAD (Holman Index >0.4) will be summarized by timepoint and at the maximum by treatment group. The denominator for the percentage of patients will be the number of patients in the population who had at least one post-baseline Holman Index measurement available. The incidence rate (per 100 patient days) of EFAD will also be calculated per treatment group.

If there are more than 5 cases of EFAD per arm, then time to develop EFAD will be analyzed using survival analysis approach (cumulative incidence), and the mean, standard error, Q1, median, Q3, minimum, and maximum for each treatment group will be displayed, where calculable. A cumulative incidence plot will also be produced. If there are less than 5 cases of EFAD in each treatment arm, then time to developing EFAD will be summarized descriptively by treatment group using n, mean, standard deviation, minimum, Q1, median, Q3, and maximum. If no events occur, then time to EFAD will not be calculated.

A spaghetti plot consisting of Holman index values over time will be produced with one line representing each patient, and different types of lines or symbols (e.g. solid and dashed) representing each treatment group. Two bolded lines will be added at y=0.2 and y=0.4 to represent the bounds for being at risk of EFAD and developing EFAD.

As a supportive analysis to the primary endpoint, the following will be analyzed:

• FA profiles will be summarized using descriptive statistics (number of patients, mean, standard deviation, median, minimum, and maximum) in each of the 2 treatment groups (Clinolipid vs Intralipid), as well as descriptive statistics of genetic polymorphisms in the FADS1 and FADS2 genes for the patients with buccal swabs with the 5 highest and 5 lowest arachidonic acid values in each treatment group.

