7.2.3 Standard-of-Care Procedures

The following procedures will be performed at intervals determined by the SOC at each investigational site (refer to Appendix 1, Schedule of Events Table):

- Laboratory evaluations including:
 - hematology complete blood count
 - chemistry basic metabolic panel and electrolytes
- Diagnosis of neonatal morbidities including bronchopulmonary dysplasia (BPD), retinopathy of prematurity (ROP), intraventricular hemorrhage (IVH), periventricular leukomalacia (PVL), necrotizing enterocolitis (NEC), and late-onset sepsis in enrolled premature infants born at 24 to <37 weeks of gestation up to 1 month CA with a birth weight ≥750g.

7.2.4 Days 15, 30, 45, 60, 75 and 90 or End of Study Treatment Procedures

The Study Treatment Period starts when the patient receives study treatment. End of study treatment is defined as the last day of PN with Intralipid or Clinolipid; maximum 90 days of study treatment is allowed.

The following procedures will be performed approximately every 15 days ± 2 days for patients continuing on PN (days 15, 30, 45, 60, 75 and 90) and within ± 2 days of the last day of study treatment (maximum 90 days on either Clinolipid or Intralipid) whenever that occurs:

- Physical examination including weight, length or height (and head circumference for infants <1 year of age)
- Vital signs
- Concomitant medications
- Concomitant procedures
- AEs
- Laboratory evaluations including:
 - Hematology parameters
 - Serum chemistry parameters
 - Hepatic integrity parameters
 - Total and direct bilirubin
 - Triglyceride levels
 - FA profile
 - Holman Index
 - Phytosterol, cholesterol, and squalene levels

In addition, the following data will be collected at end of study treatment:

 Diagnosis of neonatal morbidities including bronchopulmonary dysplasia (BPD), retinopathy of prematurity (ROP), intraventricular hemorrhage (IVH), periventricular leukomalacia (PVL), necrotizing enterocolitis (NEC), and lateonset sepsis in enrolled premature infants born <37 weeks of gestation up to 1 month CA.

After end of study treatment (maximum of 90 days), the patient will receive nutritional intervention as prescribed by their healthcare provider as SOC if PN is still required.

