1.4 Study Design

1.4.1 Overall Study Design and Plan

This is a multi-center, randomized, double-blind, controlled, safety and efficacy study to evaluate the occurrence of EFAD (diagnosed by Holman Index >0.4) in pediatric patients receiving either Clinolipid or standard-of-care soybean oil-based ILE (Intralipid) in the hospital setting from 7 up to 90 days as part of PN. The risk of developing liver disease, including PNALD (defined by direct bilirubin $\geq 2 \text{ mg/dL}$) when no other etiology for liver dysfunction is present, also will be assessed.

Approximately 100 pediatric patients, including neonates, will participate in the study. Patients will be randomized in a 1:1 ratio to the treatment groups (Clinolipid or Intralipid) according to a central dynamic randomization scheme stratified by site and age group (premature infants born <37 weeks of gestation, full-term neonates born \geq 37 weeks of gestation to <1 month of age, infants 1 to <12 months of age, children 1 to <10 years of age, adolescent 10 to <18 years of age). In the case of multiple birth pregnancies, the infants will be assigned to the same treatment group.

Holman Index and FA profile will be evaluated. Select polymorphisms in the FA desaturase genes FADS1 and FADS2, will be determined in a subset of patients. The major plasma phytosterols found in the ILEs (stigmasterol, campesterol, sitosterol), cholesterol, and squalene will also be assessed.

The study consists of a Screening Period to confirm the patient's eligibility for the study after the informed consent form (ICF) and assent (if applicable) is signed and a Treatment Period, where study Day 1 is defined as the first day the patient receives study treatment.

End of study treatment is defined as the last day of PN with Intralipid or Clinolipid; maximum 90 days of study treatment is allowed.

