1.4.2 Determination of Sample Size

The sample size of 100 patients (50 in each of the 2 treatment groups: Clinolipid vs Intralipid), including neonates, is based on the feasibility of timely enrollment of patients for generating reference data and summary descriptive statistics, rather than on a formal power calculation. No formal hypothesis testing is planned.

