2.1.2 Visit Windows

The study visits can be obtained from the eCRF and need not be derived programmatically. The visits will be displayed as: Screening, Day 1 (Baseline), Day 2, ... Day 14, Day 15, Day 30, Day 45, Day 60, Day 75, Day 90/End of treatment (EOT).

Results from unscheduled visits will not be included in table summaries. These values will only be presented in the listings.

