2.6.2 Handling of Dropouts or Missing data

All data collected up to the point where the patient drops out will be used for analyses.

Aside from missing weight in the calculation of nutritional intake, no missing data will be imputed for this study.

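### The by-visit EFAD and at-risk percentages use the any-post-baseline denominator, so at Days 15 to 75 they are diluted as patients leave PN; the maximum row is unaffected

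*SAP*

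**What the plan says.** SAP 2.4.1.2 says that the frequency and percentage of patients in the at-risk band and above 0.4 "will be summarized by timepoint and at the maximum by treatment group". The next sentence gives the only denominator rule: the "denominator for the percentage of patients will be the number of patients in the population who had at least one post-baseline Holman Index" measurement. Neither that section nor the general principles in SAP 2.1 gives a separate rule for the by-timepoint rows.

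Four other passages matter here:

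- **The event.** Under SAP 2.4.1.1 a patient counts as an EFAD case "if they have a Holman Index >0.4 at any timepoint during the study treatment". This corresponds to the maximum row.
- **Who is sampled.** Protocol 7.2.4 schedules the Holman Index "for patients continuing on PN (days 15, 30, 45, 60, 75 and 90) and within ± 2 days of the last day of study treatment". Treatment length varies by patient, and "maximum 90 days of study treatment is allowed" (SAP 1.4.1).
- **How visits are labelled.** SAP 2.1.2 lists the post-baseline visits after the daily ones as "Day 15, Day 30, Day 45, Day 60, Day 75, Day 90/End of treatment (EOT"). The final label therefore pools Day 90 with end of treatment, whenever that occurs.
- **Missing values.** Apart from weight in the intake calculations, "no missing data will be imputed for this study" (SAP 2.6.2).

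**The concern.** The denominator is fixed across visits, while the group that can supply a numerator shrinks. A patient whose PN ends at Day 9 has an end-of-treatment sample and so belongs to the denominator. That patient has no Day 60 sample and cannot be counted as a case at Day 60. The Day 60 row in effect treats the patient as measured and free of EFAD.

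These rows belong to the primary endpoint analysis, and the objective covers 7 to 90 days of treatment. A reader will look at them to see whether EFAD becomes more common with longer exposure. Under the stated rule they can show a decline produced by attrition alone.

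The alternative view over time is conditional. SAP 2.4.1.2 runs the cumulative incidence analysis only with more than 5 EFAD cases per arm; with fewer than 5 in each arm, time to EFAD is only described. In that second case the by-visit rows are the only planned EFAD percentages over time.

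**Working it through.** The plan states no expected EFAD rate, no distribution of PN duration and no by-visit percentage, so there is no figure of its own to reproduce. The check is a comparison of two proportions.

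**Notation, for one arm**

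- D = patients with any post-baseline Holman Index (the SAP denominator)
- m = patients with a Holman Index at the visit in question
- x = patients above 0.4 at that visit

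**Formula**

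- SAP percentage = x/D
- Percentage among those measured = x/m
- Hence SAP percentage = (x/m) × (m/D)

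Anyone measured at a post-baseline visit is also in D, so m/D cannot exceed 1. The SAP percentage is therefore never above the percentage among those measured, and is below it whenever m < D and x > 0.

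**Single-visit illustration (all counts assumed), D = 45**

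- m = 10, x = 2: 2/10 = 20.0% among those measured; 2/45 = 4.4% under the SAP.
- m = 20, x = 2: 2/20 = 10.0% among those measured; 2/45 = 4.4% under the SAP.

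**Course over time.** Take D = 50 (the planned arm size in SAP 1.4.2, assuming everyone has a post-baseline value) and an assumed constant 10% among those measured. With m as the denominator every visit shows 10%. With the SAP denominator the expected percentage is 10% × m/50:

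| Assumed exit from PN | Measured at Days 15/30/45/60/75 | SAP percentage at Days 15/30/45/60/75 |
|---|---|---|
| Slow | 45/40/35/30/25 | 9.0/8.0/7.0/6.0/5.0 |
| Medium | 40/25/15/10/5 | 8.0/5.0/3.0/2.0/1.0 |
| Fast | 30/12/6/3/2 | 6.0/2.4/1.2/0.6/0.4 |

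At an assumed 5% or 20% the entries halve or double; the shape does not change.

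**Rows that do not behave this way**

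- *Maximum row.* If 6 of 50 patients ever exceed 0.4, the result is 6/50 = 12.0% however many attend each visit.
- *Pooled Day 90/EOT row.* Early leavers contribute their last sample here. At 10% prevalence with 50, 48 or 45 of 50 sampled, it shows 10.0%, 9.6% or 9.0%.
- *Incidence rate and time to EFAD.* SAP 2.4.1.1 builds these from patient-days and from event or censoring dates. D does not enter.
- *Baseline row.* Patients with a baseline value and none later are left out of the denominator. An end-of-treatment sample is planned for every patient, so few should be lost this way.

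**The case against.** Three stronger readings are tempting, and the documents do not support them.

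1. *The reported EFAD risk shrinks toward zero.* A reader might infer this because the rule sits in the primary endpoint section. The patient-level event is EFAD at any time on treatment, and for that row the denominator is suitable. The rate and time-to-event analyses do not use it.
2. *Every visit is diluted.* The pooled Day 90/EOT row collects the final sample of patients who stopped early, so it is close to complete.
3. *The dilution is larger in the Clinolipid arm.* Protocol 6.14 does discontinue Clinolipid patients who need Intralipid as rescue. Under Protocol 6.8.3, however, the switch follows EFAD that persists despite maximal lipid intake. Such a patient would normally already have a value above 0.4, counted in an earlier row and in the maximum row. Unequal retention can create an apparent difference between arms: 4 of 20 measured against 2 of 10 measured is 20.0% in each, but 8.0% against 4.0% when both are divided by 50. The documents do not show that retention will differ, or in which direction.

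The best defence of the plan has two parts. First, the fixed denominator estimates something definable: the share of the evaluable cohort observed with EFAD at a visit. The alternative conditions on still receiving PN, which is a selected group. The caution about selection stands. The defence does not rescue the rule, because patients who were not measured are counted as free of EFAD.

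Second, the planned outputs allow recovery. SAP 2.4.1.2 reports frequencies, gives n with the Holman Index summaries by timepoint and plots every patient's values, and a patient-level listing is planned. A careful reader could recompute x/m. This limits the harm but does not make the printed percentage right. The study is also descriptive, with no hypothesis test resting on these rows.

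**Conclusion.** The point holds for the by-timepoint at-risk and EFAD percentages at Days 15 to 75. Read as written, SAP 2.4.1.2 dilutes each of them by m/D, and they can appear to fall when prevalence among those measured is flat. The direction is certain wherever m < D and there is at least one case. The size is not known: it depends on PN duration, which the documents do not give, and every percentage above rests on assumed counts. Under those assumptions a constant 10% would be printed at Day 75 as anything from 5.0% (slow exit) to 0.4% (fast exit).

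The effect on the baseline row is minor, and on the pooled Day 90/EOT row small. The patient-level primary result, the incidence rate and time to EFAD stand as planned. This is a stated rule that misleads in supporting rows of the primary table; it does not invalidate the primary result.

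**What to change.** Replace the denominator sentence in SAP 2.4.1.2 with:

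*For each timepoint, the denominator is the number of patients with a non-missing Holman Index at that timepoint. For the post-baseline maximum, it is the number of patients with any post-baseline Holman Index. Each percentage is shown with n/m.*

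Apply this to the EFAD tables for both the FAS and the PPS (14.3.5.1.1 and 14.3.5.1.2).

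The cost is one sentence and a small programming change before the tables are run; no new data are needed. The downside is that late-visit percentages will rest on few patients and will describe only those still on PN, so the printed m is needed to read them.

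The same edit is a good occasion to settle a neighbouring mismatch. Protocol 9.5 divides the overall EFAD proportion by all patients in the group, SAP 2.4.1.2 divides by those with a post-baseline value, and SAP section 3 declares no change from the protocol. The two should be reconciled or the change declared.
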